4.6.3.2. Systemic Hypersensitivity Reactions (including cytokine release syndrome)

A search will be performed using the current MedDRA version Standardised MedDRA Queries (SMQs) to search for relevant events, using the following queries:

- Anaphylactic reaction SMQ (20000021)
- Hypersensitivity SMQ (20000214)
- Angioedema SMQ (20000024)

Events that satisfy the queries will be listed, by temporal order within patient ID, and will include SOC, PT, SMQ event categorization including detail on the scope (narrow or broad), reported AE term, AE onset and end dates, severity, seriousness, outcome, etc.

4.6.3.3. Malignancies

Malignancies will be identified using terms from the malignant tumors SMQ (SMQ 20000194). Malignancies excluding nonmelanoma skin cancers (NMSC) and NMSC will be reported separately.

A listing including all malignancy cases will be provided. An NMSC flag will be provided using the following MedDRA PTs (the list will be updated depending on the MedDRA version used for analysis):

- Squamous cell carcinoma of skin (10041834)
- Bowen's disease (10006059)
- Basal cell carcinoma (10004146)
- Basosquamous carcinoma (10004178)
- Basosquamous carcinoma of skin (10004179)
- Squamous cell carcinoma (10041823)
- Skin squamous cell carcinoma metastatic (10077314)
- Skin cancer (10040808)
- Carcinoma in situ of skin (10007390)

The number and percentage of patients with TEAE-associated malignancies excluding NMSC and NMSC will be summarized by treatment group. In addition, the IR (for detail, see Section 4.6) and 95% CI will be calculated for the overall observation time. All cases identified by malignant tumors SMQ will be assessed after database lock by the medical team to determine (1) confirmed NMSC cases and (2) symptom and date that triggered the malignancy investigation or diagnosis. An additional listing based on medical review may also be provided if deemed necessary. All cases reported in the study database or by Lilly Safety System (LSS) report, disregarding the length of gap between the last treatment dose date and the event date will be included.

4.6.3.4. Gastrointestinal Perforations

Treatment-emergent adverse events potentially related to gastrointestinal (GI) perforations will be analyzed using reported AEs. Identification of these events will be based on the PTs of the MedDRA Gastrointestinal Perforations SMQ (SMQ 20000107); note that this SMQ holds only narrow terms and has no broad terms. Potential GI perforations identified by the above SMQ search will be provided as a listing for internal review by the medical safety team. Each case will be assessed to determine whether it is a GI perforation. Frequency and relative frequency for each PT will be provided, ordered by decreasing frequency in the LY3471851 1800µg treatment group. Comparisons between each LY3471851 treatment group and placebo will be made using Fisher's exact test.

4.6.4. Injection Site Reaction

If a participant spontaneously reports symptoms of an injection site reaction, an authorized member of the site staff who, in the opinion of the investigator, is qualified to assess reports of potential ISRs and who is not involved with any other study procedure will evaluate the participant's report.

The number and percentage of patients who experienced ISR will be summarized by treatment group and by visit. The number and percentage of patients with the following ISR records will be summarized by treatment group and by visit. Details about ISR records are referred to the Case Report Form (CRF).

- Anatomical location of the injection site reaction
- Abdomen Side
- Directionality of the anatomical location of the administration
- Arm side
- Whether the subject has any injection site erythema (reddening) or not
- Severity of the injection site erythema
- Whether the subject has any injection site induration (hardening or thickening of tissue) or not
- Severity of the injection site induration
- Whether the subject has any injection site pain (including burning) or not
- Severity of the injection site pain
- Whether the subject has any injection site pruritus
- Severity of the injection site pruritus

- Whether the subject has any injection site edema (swelling or accumulation of fluid in tissues at height above normal skin) or not
- Severity of the injection site edema
- When the Injection related event occurred in relationship to the study treatment

Ordinal logistic regression will be used for the ordinal ISR reported. The frequency of the maximum severity of ISRs will be summarized by treatment group.

4.6.5. Clinical Laboratory Evaluation

Laboratory evaluations will be summarized and analyzed for the following periods:

- Induction Period,
- Maintenance Period,
- Extension Period (including Extension Induction and Extension Maintenance)

All laboratory tests will be presented using the Système International of units (SI) and conventional (CN) units. For topics of safety in special groups and circumstances, laboratory test units will be specified for each analysis.

Lilly Large Clinical Trial Population Based (LCTPB) reference limits will be used to define the low and high limits because it is generally desirable for limits used for analyses to have greater specificity (identify fewer false positive cases) than reference limits used for individual patient management. When Lilly LCTPB reference ranges are unavailable, then central laboratory (Labcorp) reference ranges will be used. For the 4 key hepatic laboratory assessments (alanine aminotransferase [ALT], aspartate aminotransferase [AST], total bilirubin, and alkaline phosphatase [ALP]), central laboratory reference ranges (Labcorp) will be used and all results pertaining to these assessments will be included as a separate analysis to address the risk of liver injury as a special safety topic (see Section 4.6.3.1). Central laboratory reference ranges (Labcorp) will also be used to evaluate immunoglobulins and lymphocyte cell subsets (see Sections 4.6.5.2 and 4.6.5.6). See 6.10 for details of the reference range by laboratory analytes.

The low-density lipoprotein/high-density lipoprotein (LDL/HDL) ratio will be derived as the ratio of LDL cholesterol to HDL cholesterol. There are no Lilly LCTPB reference ranges or central lab reference ranges for the LDL/HDL ratio.

The following will be conducted for laboratory analyte measurements collected quantitatively:

- Box plots for observed values: Values at each visit (starting at randomization) and change from baseline to each visit and to last postbaseline measure will be displayed in box plots for patients who have a baseline and at least 1 postbaseline visit. For visits included in the treatment period, patients will be included only if the visit occurs on or before the date of treatment discontinuation/completion. Follow-up visit will be the first visit that occurred during the Follow-up period. Individual measurements outside of reference limits will also be displayed using distinct symbols overlaying the box plot. Original-scale data will be used for the display but for some analytes (e.g., immunoglobulins) a logarithmic scale will be used to aid in viewing the measures of central tendency and dispersion. Unplanned measurements will be excluded. Descriptive summary statistics will be included in a table below the box plot. These box plots will be

used to evaluate trends over time and to assess a potential impact of outliers on central tendency summaries. A p-value for change from baseline to endpoint will be provided using an ANCOVA model with explanatory term for treatment and the baseline value as a covariate. Endpoint will be the last observation where patient is on treatment.

- Treatment-emergent high/low analyses: The number and percentage of patients with treatment-emergent high and low laboratory results at any time will be summarized by treatment group. Planned and unplanned measurements will be included. A treatment-emergent **high** result is defined as a change from a value less than or equal to the high limit at all baseline visits to a value greater than the high limit at any time during the treatment period and up to 60 days after treatment discontinuation. A treatment-emergent **low** result is defined as a change from a value greater than or equal to the low limit at all baseline visits to a value less than the low limit at any time during the treatment period and up to 60 days after treatment discontinuation. The Fisher's exact test will be used for the treatment comparisons.

For laboratory analyte measurements collected qualitatively, a listing of abnormal findings will be created. The listing will include patient ID, treatment group, laboratory collection date, analyte name, and analyte finding.

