The randomization ratios are described in Section 1.2.1.

Study Periods

This study has multiple periods.

Screening period

This period begins with Visit 1, which occurs 5 weeks (or less) before the planned randomization visit. A participant's screening evaluations must be completed and reviewed to confirm the participant's eligibility before randomization and dosing occurs at Visit 2.

Blinded induction and blinded maintenance periods

The double-blind, placebo-controlled, 12-week induction treatment period begins at Visit 2. Dosing, sample collection, and assessments continue Q2W, as shown in the SOA in the protocol. Between Week 12 and Week 14, based on samples and assessments collected at Week 12, participants will be classified as either "Week 12 Responders" or "Week 12 Nonresponders" based on the "clinical response" criteria defined in the protocol.

- "Week 12 Responders" will continue to receive their same randomly assigned treatment throughout the blinded 40-week Maintenance Period, with the final dose occurring at Week 50 and the last maintenance assessments and sample collections at Week 52.
- "Week 12 Nonresponders" will enter the Extension Induction and Extension Maintenance Periods.

Extension induction and maintenance periods

Beginning at Week 14, participants who were classified as Week 12 Nonresponders will receive the high dose (CC1 μg) of LY3471851 Q2W, unless a lower dose is selected for Stage 2 based on interim analyses.

Between Week 26 and Week 28, based on samples and assessments collected at Week 26, these participants will again be classified according to their clinical response status based on MMS (responder or nonresponder).

- Participants who are classified as responders based on the samples and assessments at Week 26 will continue to receive LY3471851 Q2W as maintenance through the remainder of the study. These participants have their final dose at Week 50 and their last maintenance assessments and sample collections at Week 52.
- Participants who are classified as nonresponders based on the Week 26 samples and assessments will be permanently discontinued from study drug when his/her status as a nonresponder has been determined; such participants will enter the post-treatment follow-up period.

Post-treatment follow-up period

[figure not shown]

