4.1. General Considerations

This SAP is intended to describe the analyses of all objectives, as well as safety assessments, for study KFAH.

Statistical analysis of this study will be the responsibility of Eli Lilly and Company (hereafter Lilly) or its designee. For primary and key secondary objectives, statistical analyses will be performed using SAS® Enterprise 7.1 or higher, SAS® Version 9.4 or higher, or RStudio Server Pro Version R.3.6.3. or higher.

Efficacy analyses will be conducted on the mITT population. Safety analyses will be conducted on the Safety population (same as mITT population, as described in Section 3). The efficacy analysis of the primary endpoint and secondary endpoints will be repeated for ITT population. Additional safety analyses may be performed as deemed appropriate.

The baseline modified Mayo Score (MMS) is calculated from valid daily diary entries obtained prior to endoscopy during the screening period and the endoscopic appearance of the mucosa at this screening endoscopy. For other efficacy, health outcome and safety assessments, baseline is defined as the last non-missing assessment recorded on or prior to the date of the randomization visit (Visit 2).

Any change to the data analysis methods described in the protocol will require an amendment ONLY if it changes a principal feature of the protocol. Any other change to the data analysis methods described in the protocol and the justification for making the change will be described in the clinical study report. Additional exploratory analyses of the data will be conducted as deemed appropriate.

Not all displays and analyses described in this SAP will necessarily be included in the CSR. Not all displays will necessarily be created as a “static” display. Some displays may be incorporated as interactive display tools instead of or in addition to a static display. Any display described in this SAP and not provided in CSR would be available upon request.

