4.6.1. Extent of Exposure

Duration of exposure to study treatment (defined as time since first injection of study treatment in days) will be summarized by treatment group during the Induction Period, the Maintenance Period, and the Extension Period.

Duration of exposure during the Induction Period for the Safety Population will be calculated as:

(Disposition date (for those who have discontinued the Induction Period), OR Maintenance/Extension Start date -1 (for those who have completed the Induction Period), OR Date of last study visit in the Induction Period (for those who are still being treated in the Induction Period) – Date of first injection of study treatment + 1)

Duration of exposure during the Maintenance Period will be calculated as:

(Disposition date (for those who have discontinued the Maintenance Period), OR Date of last study visit in the Maintenance Period (for those who are still being treated in the Maintenance Period) – Date of the Visit 10 injection of study treatment + 1)

Duration of exposure to LY3471851 during the Extension Period will be calculated as:

(Disposition date (for those who have discontinued the Extension Period), OR Date of last study visit in the Extension Period (for those who are still being treated in the Extension Period) – Date of the Visit 10 injection of study treatment + 1)

Duration of exposure to LY3471851 for the combined Induction Period and Maintenance Period will be calculated as:

(Disposition date (for those who have discontinued the Maintenance Period), OR Date of last study visit in the Maintenance Period (for those who are still being treated in the Maintenance Period)– Date of first injection of LY3471851 + 1)

Duration of exposure to LY3471851 for the combined Induction Period and Extension Period will be calculated as:

(Disposition date (for those who have discontinued the Extension Period), OR Date of last study visit in the Extension Period (for those who are still being treated in the Extension Period)– Date of first injection of LY3471851 + 1)

The date of first injection of LY3471851 is defined in [Table KFAH.4](#)**Error! Reference source not found.**

Table KFAH.4. First Injection of LY3471851 by Treatment Group

	Visit of first LY3471851
All patients randomized to LY3471851 (regardless of Week 12 response status)	Week 0 (Visit 2)
Week 12 Inadequate Responders originally randomized to placebo and assigned to LY3471851 at Visit 10	Week 14 (Visit 10)

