4.6.6. Vital Signs and Other Physical Characteristics

Vital signs and physical characteristics include systolic blood pressure (SBP), diastolic blood pressure (DBP), pulse, weight, BMI, and body temperature. Original-scale data will be analyzed. When these parameters are analyzed as continuous numerical variables, unplanned measurements will be excluded. When these parameters are analyzed as categorical outcomes, planned and unplanned measurements will be included.

Vital signs and physical characteristics will be summarized and analyzed for the following periods:

- Induction Period

- Maintenance Period
- Extension Period

The planned analyses described for the laboratory analytes in Section 4.6.5 will be used to analyze the vital signs and physical characteristics.

Table KFAH.5 defines the low and high baseline values as well as the criteria used to define treatment-emergence based on postbaseline values. Postbaseline values include all values after baseline in the treatment and follow-up periods. The blood pressure and pulse rate criteria are consistent with the document *Selected Reference Limits for Blood Pressure, Orthostasis, and ECG Numerical Parameters (Including Heart Rate) for Use in Phase II-IV Clinical Trials Version 1.1* approved on 8 March 2013 as recommended by the Lilly Cardiovascular Safety Advisory Committee (CVSAC).

Table KFAH.5. Categorical Criteria for Abnormal Treatment-Emergent Blood Pressure and Pulse Measurement, and Categorical Criteria for Weight Changes for Adults

	Low	High
Systolic Blood Pressure (mm Hg)	≤ 90 (low limit) and decrease from lowest value during baseline ≥ 20 if > 90 at each baseline visit	≥ 140 (high limit) and increase from highest value during baseline ≥ 20 if < 140 at each baseline visit
Diastolic Blood Pressure (mm Hg)	≤ 50 (low limit) and decrease from lowest value during baseline ≥ 10 if > 50 at each baseline visit	≥ 90 (high limit) and increase from highest value during baseline ≥ 10 if < 90 at each baseline visit
Pulse (beats per minute)	< 50 (low limit) and decrease from lowest value during baseline ≥ 15 if ≥ 50 at each baseline visit	> 100 (high limit) and increase from highest value during baseline ≥ 15 if ≤ 100 at each baseline visit
Weight (kilograms)	(Loss) decrease $\geq 7\%$ from lowest value during baseline	(Gain) increase $\geq 7\%$ from highest value during baseline

[figure not shown]
Abbreviation: mm Hg = millimeters of mercury.

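### Extension Period laboratory and vital-sign analyses keep the Visit 2 baseline for placebo nonresponders who first receive LY3471851 at Visit 10, so persisting placebo-period abnormalities are scored as emergent while everyone is on drug

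*SAP*

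**What the plan says.** SAP 4.1 gives a special baseline for the modified Mayo score. Its general rule, which covers the remaining data including safety, reads: "baseline is defined as the last non-missing assessment recorded on or prior to the date of the randomization visit (Visit 2". Protocol 9.4.1 says the same.

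SAP 4.6.5 lists the periods for which laboratory data are analysed, among them the "Extension Period (including Extension Induction and Extension Maintenance". Within each period it plans change from baseline (box plots, and ANCOVA to the last on-treatment value) and treatment-emergent high and low results. The starting condition for an emergent high result reads "a change from a value less than or equal to the high limit at all baseline visits". The outcome condition that completes the rule reads "to a value greater than the high limit at any time during the treatment period and up to 60 days after treatment discontinuation".

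SAP 4.6.6 lists the same periods for vital signs, weight and BMI and carries the rules over: "The planned analyses described for the laboratory analytes in Section 4.6.5 will be used to analyze the vital signs and physical characteristics". It adds: "Postbaseline values include all values after baseline in the treatment and follow-up periods".

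On treatment in the extension, SAP 1.2 states that "participants who were classified as Week 12 Nonresponders will receive the high dose" from Week 14, unless a lower dose is chosen after interim analysis. In either case the drug is LY3471851. For exposure, Table KFAH.4 in SAP 4.6.1 sets the first LY3471851 injection at Week 14 for "Week 12 Inadequate Responders originally randomized to placebo and assigned to LY3471851 at Visit 10".

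**The concern.** For participants randomised to LY3471851, Visit 2 is both the baseline visit and the first day of drug, so the general rule works. For placebo nonresponders the two dates are about 14 weeks apart. The SAP recognises the later start when it computes exposure, but not when it defines baseline.

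Two things follow. First, a value that was normal at baseline, went out of range on placebo and is still or again out of range in the extension is scored as emergent in a period when all participants receive LY3471851. This group consists of people whose colitis did not respond on placebo, so disease-related drift in blood counts or weight is plausible. Second, their change from baseline adds placebo-period change to drug-period change.

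The rule can also hide a signal. A participant abnormal at a baseline visit, normal just before the Visit 10 dose and abnormal again on drug can never be counted.

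**Working it through.** There is no stated figure to reproduce. The check is a reading of the rules in sequence, followed by an illustration on assumed inputs.

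**Rules in sequence**

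1. Baseline for safety data is fixed at or before Visit 2 (SAP 4.1; protocol 9.4.1). Neither document resets it at Visit 10 for laboratory or vital-sign data.
2. The emergent analyses are run for the Extension Period (SAP 4.6.5, 4.6.6). Lymphocyte subsets (4.6.5.2) and immunoglobulins (4.6.5.6) use the same approach by reference.
3. The reference state is normality at every baseline visit. The outcome window is the treatment period plus 60 days for laboratory results, and all values after baseline for vital signs. Neither window is limited to values after the first LY3471851 dose.
4. Protocol Table 1 schedules a dose at Visit 9 (Week 12), and Table KFAH.4 starts LY3471851 at Visit 10 (Week 14). Placebo exposure therefore covers about 14 weeks.
5. Protocol Section 8 has assessments completed before dosing. The Visit 10 sample, which Table 3 places in the extension schedule, is therefore still a placebo-exposed value, yet nothing excludes it as an Extension outcome.

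Take a placebo nonresponder with a normal analyte at baseline, a high value at Week 12 and a high value at an Extension visit. Under the stated rule this is emergent in the Extension Period. With baseline at the last value before the Visit 10 dose, and that value also high, it is not. For weight, Table KFAH.5 counts a loss of at least 7% from the lowest baseline value, and part of that loss may have occurred on placebo.

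**Illustration**

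Input from the documents: about 40 placebo participants at end of study (SAP 5). All other inputs are assumed:
- placebo clinical response of 10% to 40%, with no Induction dropout;
- everyone normal at Visit 2;
- a = share who became abnormal on placebo and are still abnormal in the extension, 5% to 15%;
- b = share of the remainder who become newly abnormal after Visit 10, 5% or 10%.

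Entrants: 40 × (1 − 0.40) = 24 to 40 × (1 − 0.10) = 36.

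Incidence under the SAP rule = a + (1 − a) × b. Incidence with a reset baseline, among those normal before the Visit 10 dose = b.

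| a | b | SAP rule | Reset baseline |
|---|---|---|---|
| 5% | 5% | 0.05 + 0.95 × 0.05 = 9.8% | 5.0% |
| 15% | 5% | 0.15 + 0.85 × 0.05 = 19.2% | 5.0% |
| 5% | 10% | 0.05 + 0.95 × 0.10 = 14.5% | 10.0% |
| 15% | 10% | 0.15 + 0.85 × 0.10 = 23.5% | 10.0% |

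The excess count is N × a: from 24 × 0.05 = 1.2 to 36 × 0.15 = 5.4 participants per analyte. Any Induction dropout lowers it.

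**The case against.** The best reply is that sections 4.6.5 and 4.6.6 never say in words which baseline the Extension analyses use, so the gap might be called missing detail, with a period baseline implied. That does not hold. SAP 4.1 states a general rule for safety assessments, and without an exception it governs.

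Other parts of the reply do stand.

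- A reader might infer that these results will be tabulated in LY3471851 columns. The SAP does not settle this. Section 3 analyses participants by assigned treatment, and 4.6.1 keeps dose-modified participants under the randomised arm (for exposure), which suggests a separate former-placebo column. Table KFAH.4, however, speaks of assignment to LY3471851 at Visit 10. Under either label the table describes time on drug and would contain placebo-period abnormalities.
- A reader might infer that the only within-person view of starting the drug is lost. It is not. Everyone randomised to LY3471851 starts at Visit 2, and their change from baseline has concurrent placebo during Induction.
- A reader might infer damage to the randomised safety comparison. There is none. The Extension Period has no concurrent placebo group, so the Fisher and ANCOVA p-values planned in 4.6.5 have no randomised placebo contrast there to distort.
- The plots of observed values by visit may show part of the change before Visit 10. The hepatic threshold counts, eDISH plot and Hy's rule listing in 4.6.5.1 do not use the baseline-normality rule.

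These points limit the consequence. They do not correct the emergent counts or the change from baseline.

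**Conclusion.** The point holds as a defect in a stated rule. For placebo nonresponders, Extension Period emergence and change from baseline are measured from Visit 2 although drug starts at Visit 10. The misclassification covers abnormalities that arose on placebo and persist or recur at an Extension measurement; those resolved by then should not count if only Extension values are used. The effect is confined to uncontrolled Extension safety summaries.

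Its size cannot be derived, because the documents give no placebo clinical response rate, dropout rate or abnormality rate. The range of about 1 to 5 participants per analyte shows only what the assumed inputs imply. The change is worth making before unblinding, since choosing a baseline afterwards would be an unplanned analytic decision.

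**What to change.** Add to SAP 4.6.5 and 4.6.6, for Extension Period laboratory, vital-sign and weight analyses of participants first dosed with LY3471851 at Visit 10:

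1. Baseline is the last non-missing value before that dose. This is the Visit 10 pre-dose value where one is scheduled (protocol Table 3 has hematology, chemistry, urinalysis, vital signs and weight), and otherwise the Week 12 value, for example for lipids and flow cytometry.
2. For emergence, require normal values at a named set of pre-dose visits, for example Week 12 and Visit 10, and name the set for analytes not drawn at Visit 10. A single pre-dose value would be a looser standard than the existing requirement of normality at every baseline visit.
3. Count only values after the Visit 10 dose.
4. State the Extension group labels, and show placebo-to-LY3471851 participants in a separate column from nonresponders already on LY3471851.

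The cost is one SAP definition, a programming flag and table labels. No new samples or visits are needed.
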